Study protocol and statistical analysis plan

Date: Apr 3, 2025

Study title:

Hypnotherapy With Audiofiles for Children and Adolescents With Disorders of Gut-brain Interactions in Sweden -a Feasibility Study

Scientific Summary

Background:

Functional gastrointestinal disorders (FGID) with abdominal pain, such as Irritable Bowel Syndrome (IBS), affect 10–25% of all children and adolescents in Sweden. These conditions are often associated with high school absenteeism, reduced quality of life, and frequent healthcare use. For children and adolescents with IBS, various psychosocial treatments are the only interventions that have shown good effect in scientific studies, while pharmacological treatments have had limited or no effect. In Sweden, the most commonly used and studied treatment for this patient group is exposure-based Cognitive Behavioral Therapy (CBT), which is also available as internet-delivered CBT (iCBT) in standard healthcare. However, iCBT requires therapist support from a psychologist, resulting in long wait times, and not all patients benefit. Therefore, additional evidence-based and preferably more accessible alternatives are in demand.

Hypnotherapy involving gut-directed meditation and relaxation exercises has shown good treatment effects for FGID in children and adolescents in international studies, but this form of treatment is currently not available in Sweden. Studies have also shown that home-based hypnotherapy with self-guided exercises via audio files is as effective as individual hypnotherapy, making it a cost-effective treatment. Audio files allow treatment to begin immediately after diagnosis by a physician, avoiding long wait times like those for iCBT. If hypnotherapy proves to be as effective in Swedish standard care as in international studies, it would represent a major advancement for the large and suffering group of children and adolescents with FGID.

Aim:

In an international research collaboration, we intend to translate and adapt hypnotherapy audio files — proven highly effective in a Dutch context — to Swedish conditions so that they can be used to treat children and adolescents in Sweden. The feasibility study described in this project plan is required to evaluate effect sizes and the practical aspects of the treatment. Our experience from previous treatment studies is that the insights gained from this type of feasibility study provide the knowledge needed to conduct large and successful randomized controlled trials (RCTs) in the next phase — for example, comparing hypnotherapy and iCBT in terms of effectiveness, cost-efficiency, and which patients respond best to which treatment. The overarching goal of the project is to help children and adolescents with FGID by ultimately introducing a new treatment option into standard care.

Feasibility Study Research Questions:

1. Can children and adolescents with pain-dominant FGID experience reduced gastrointestinal symptoms through hypnotherapy with audio files?
2. Can children and adolescents with pain-dominant FGID experience improved daily functioning through hypnotherapy with audio files?
3. Can children and adolescents with pain-dominant FGID experience improved quality of life through hypnotherapy with audio files?
4. What practical challenges may arise in patient recruitment, data collection, and the treatment itself (that need to be addressed before a larger RCT can be conducted)?

5. Feasibility Study Method:

A feasibility study of the hypnotherapy intervention without a control group to evaluate feasibility, acceptability, and effect sizes for the primary outcome measures.

Children (N=20–30) of school age (8–17 years) with pain-dominant FGID (defined according to the Rome IV criteria) will be recruited from a pediatric outpatient clinic in Stockholm. Measurements of, among other things, gastrointestinal symptoms, functional level, and quality of life will be conducted using validated instruments before, during (every three weeks), and after treatment.

6. Significance of the Feasibility Study:

The feasibility study will provide estimates of effect sizes for the outcome measures (required for power analysis) and offer invaluable practical experience that will make it possible to later carry out a successful large-scale clinical trial.

Project Description:

The first part of the project (which this application concerns) consists of a feasibility study in which the applicability, preliminary effectiveness, and mechanisms of action of the hypnotherapy treatment will be evaluated in a smaller patient group. The goal is to recruit 20–30 patients with a confirmed FGID diagnosis from the pediatric gastroenterology clinic at Sachsska Children's Hospital and/or other hospital-based specialist clinics at Sachsska. These patients will undergo a 12-week treatment involving hypnotherapy self-exercises using audio files at least 5 times per week. Patients and their parents will complete self-report assessments on symptom severity, quality of life, school absenteeism, etc., using standardized questionnaires via an online platform every three weeks. A table listing the outcome measures is attached.

All patients will be contacted by a gastroenterology-focused physician or nurse at the clinic or by phone (if referred from another unit) before inclusion to assess inclusion and exclusion criteria, inform the family about the study, and go over the treatment principles.

Inclusion criteria:

- Age 8–17 years
- Confirmed diagnosis of functional dyspepsia, functional abdominal pain, or IBS according to Rome IV criteria (including evaluation for organic differential diagnoses)
- Reading and writing proficiency in Swedish
- Less than 40% school absenteeism
- Stable dose (for over 1 month) if on psychopharmacological medication

Exclusion criteria:

- Non-functional medical condition
- More than 40% school absenteeism
- Ongoing psychotherapeutic treatment
- Severe psychosocial or psychiatric problems requiring more intensive care than hypnotherapy

These criteria will be assessed using questionnaires and individual interviews before treatment begins.

Data Analysis:

For the feasibility study, 20–30 patients will be recruited — the number is based on prior experience with similar pilot studies. Data will be collected every three weeks from the start to the end of treatment via a secure online service with identity verification. The same platform will be used to distribute treatment files and instructions to patients and their parents. Data will be stored in a secure database protected by two-factor authentication and access control. Once the data is no longer needed for the study, the key to the code will be destroyed (no later than 10 years after data collection).

An improvement of >30% on the primary outcome is defined as clinically significant, based on recommendations from previous studies. Although data will be collected across multiple outcomes and time points, a preliminary mediation analysis can also be conducted to assess what drives potential improvements and in which phase of treatment this occurs. Statistical analyses will be conducted by a statistician with experience in similar studies and analyses.

Data Analysis Plan:

1 Methods

The planned RCT shares many similarities with Bonnert et al. (2017) and Bonnert et al. (2014).

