1.5 Imputation of missing values

The pilot study includes 32 patients at baseline (week 0). Of these patients, there are 21 patients with complete follow-up (no missing data), 25 patients with no missing data at week 12, and 2 patients with no data after week 0. Data is rarely missing completely at random (MCAR). It is more likely to assume that there are systematic differences between the non-participating patients (i.e. the patients who at some point decided to drop out) and the participating patients, which could bias the results. For example, some patients might have discontinued the treatment due to insufficient treatment effect. If that is the case, there is a risk that the estimated effect of the treatment could be overestimated if the missing values are not handled correctly. For this reason, a sensitivity analysis was made, comparing the results of using no imputation to the results of using Last Observation Carried Forward (LOCF). A drawback of LOCF is that it underestimates the variability in the data, which can lead to too narrow confidence intervals. Another alternative is to use multiple imputation, which account for the uncertainty of estimating the missing data. However, if the observed data cannot account for the systematic differences, that is if the data is missing not at random (MNAR), multiple imputation may still lead to biased results.

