1.6 Limitations

No control group: It is important to note that since we do not have a control group to compare with, the risk of receiving biased results is high, especially due to the phenomenon known as regression toward the mean. That is, many of the patients who were in poor health at baseline (week 0) would probably have felt better at week 12 even without treatment.

No analysis of outliers: No analysis of outliers has been performed.

No comparison of models: Due to the small sample size, the decision was made to only fit an LMM with patient specific random intercepts. However, a larger sample size would enable us to use more complex models that can provide better fit to the data. In a more complex model we can for example include quadratic effects, random slopes, or interaction terms. For parent rated outcomes, we should also consider using a 3-level mixed model where we cluster the data by both parent and adolescent.

Modeling discrete variables as continuous variables: The outcome variable for pain frequency represents the number of days during a week that the individual felt pain, which means that it is a discrete variable with a minimum value of zero and a maximum value of seven. In this analysis we will model pain frequency as if it was a continuous variable using LMM for ease of interpretation. However, count data is usually modeled using Poisson regression.

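### A one-arm study cannot show what drives improvement: the offered mediation analysis cannot separate treatment from time, and the fitted model cannot locate a phase

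*Combined protocol and SAP*

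**What the plan says.** The Project Description states that "mechanisms of action of the hypnotherapy treatment will be evaluated in a smaller patient group". The Data Analysis section then says that "a preliminary mediation analysis can also be conducted to assess what drives potential improvements and in which phase of treatment this occurs". The design, under Feasibility Study Method, is "A feasibility study of the hypnotherapy intervention without a control group".

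The numbered Data Analysis Plan (sections 1.1 to 1.6) has no mediation section. It names no mediator, outcome, lag, model or confounder set for such an analysis, and no limit on the pairs examined. Section 1.1.1 writes out a model with a quadratic term and random slopes but sets it aside because of the small sample. Section 1.6 confirms that only the random-intercept model is fitted. Section 1.2 puts depression, anxiety, parental quality of life and school absence at weeks 0 and 12 only. Section 1.6 also warns that "since we do not have a control group to compare with, the risk of receiving biased results is high", citing regression toward the mean. It does not mention mediation.

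**The concern.** Mediation splits a treatment effect into a part that runs through a mediator and a remainder. That requires an effect of treatment on the mediator. Here treatment does not vary, so elapsed weeks must stand in for it, and weeks also carry spontaneous recovery and regression to the mean. A mechanism reported from this study would therefore rest on a path that the design cannot identify. Calling the analysis preliminary lowers its weight but does not make the path estimable.

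The second promise, to find the phase in which improvement occurs, is not served by the model to be fitted. At stake is the study's mechanism statement. The pre-post effect sizes do not depend on it.

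**Working it through.** The plan gives no figure for mediation, so there is none to reproduce. The check has five steps.

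**1. Treatment-to-mediator path.** Write the mediator as M = a0 + a1·WEEK + patient effect + error. Then a1 = (change without treatment) + (change due to treatment). One arm yields one slope for two unknowns. If M falls by 0.6 units over 12 weeks, a treatment share of 0 and a share of 0.6 fit the data equally well. Everyone gets the same instruction: "hypnotherapy self-exercises using audio files at least 5 times per week". Actual practice will vary, but the available text mentions no adherence measure (the attached outcome table is not reproduced), and self-chosen practice would be confounded.

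**2. Phase.** Under section 1.1.1 the expected change over any three-week interval is 3·β1, which is 3/12 = one quarter of the 12-week change, whichever interval is taken. The model imposes equal change in weeks 0–3 and weeks 9–12. Outcomes measured only at weeks 0 and 12 hold no information on phase or temporal order.

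**3. How often a false mechanism appears.** Sample sizes follow the documents: "20–30 patients will be recruited — the number is based on prior experience with similar pilot studies", while section 1.5 has 32 at baseline and "25 patients with no missing data at week 12". Five visits (weeks 0, 3, 6, 9, 12) are inferred from the three-weekly schedule. All else is assumed. The mediator M has no effect on the outcome Y in any setting.

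- Set A: n = 25 and 30; both measures fall 0.6 units; SDs of 1.0 (intercept), 0.6 (individual 12-week change) and 0.6 (residual). Random-intercept regressions of M on WEEK (slope a) and of Y on WEEK and M (coefficient b of M). Sobel test: |ab| / √(a²·SE_b² + b²·SE_a²) > 1.96.
- Set B: n = 20 to 32; both measures improve by 0.5 or 0.8 baseline SD; SDs of individual change and residual 0.6; no shared visit-level error. Within-person regression with cluster-robust errors; both paths must be significant at 5%.

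| Model for Y on M | Assumed link between M and Y | False mechanism |
|---|---|---|
| Concurrent, WEEK adjusted, random intercept (A) | none | 2–3% |
| Same (A) | intercept and slope correlations 0.5 | 23–37% |
| Same (A) | plus visit-level error correlation 0.3 | 85–93% |
| Concurrent, WEEK adjusted, within-person (B) | none | 3–7% |
| Same (B) | correlation of changes 0.8 | 9–20% |
| Concurrent, WEEK not adjusted, within-person (B) | none | 8–55% |
| Same (B) | correlation of changes 0.8 | 25–84% |
| Mediator lagged one visit, WEEK adjusted, within-person | correlations as in A | 6–8% |
| Same | correlation of changes 0.8 (B) | 9–13% |

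The lagged rows count the M-to-Y path alone. They apply to within-person estimation; a lag by itself does not remove person-level correlation from a random-intercept model.

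**4. Precision of a plain correlation of changes.** By Fisher's z, the smallest correlation with 80% power at two-sided 5% is tanh[(1.960 + 0.842)/√(n − 3)]. For n = 25 this is tanh(2.802/4.690) = 0.54; for n = 20 it is 0.59 and for n = 32 it is 0.48. An observed r of 0.5 at n = 25 has 95% limits tanh(0.549 ± 1.960/4.690) = 0.13 to 0.75.

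**5. Number of pairs.** With five measures (assumed) there are 5·4/2 = 10 pairs. If the tests were independent at 5%, the chance of at least one false finding is 1 − 0.95^10 = 40%.

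**The case against.** The strongest reply is that the analysis is optional and preliminary. None of the four research questions concerns mechanism. Section 1.6 can be read as a study-wide warning, and section 1.4 cautions against too many tests. Three-weekly data would also allow a lagged within-person analysis, which does inform temporal order. All of this limits the severity. It does not answer the point: the Project Description says without qualification that mechanisms will be evaluated, no lagged model is specified, and a lag does not supply the missing treatment contrast.

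Four stronger readings are tempting, and the documents do not support them.

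- *Any two measures that improve together will pass as a mechanism.* Joint improvement alone gives 2–7% once WEEK is adjusted for. The excess comes from correlated individual changes, from shared visit-level error, or from leaving WEEK out.
- *The false-positive rate is about 90%.* That figure belongs to one concurrent model with an assumed error correlation of 0.3. The plan specifies no model, and shared reporting error cannot be presumed: both patients and parents report, no mediator is named, and the outcome table is not shown.
- *A comparator would cure everything.* Randomisation protects the treatment-to-mediator path. It does not protect the mediator-to-outcome path, where shared reporting error acts, so the highest figures are not evidence about the one-arm design as such.
- *A false mechanism would select the measures for the RCT.* The plan says that effect sizes and practical experience carry forward. It does not give the mediation result that role.

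**Conclusion.** The point holds as a mismatch between what the plan says it can conclude and what the design can identify. With constant treatment, a treatment-to-mediator effect cannot be separated from time, natural course and regression to the mean, and the linear random-intercept model cannot locate a phase. Neither conclusion rests on a simulation assumption.

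The size of the error risk does rest on assumptions. It is near nominal when individual changes are unrelated and WEEK is adjusted for, roughly 6–13% with a lagged mediator and within-person estimation, and up to about 90% for a concurrent model with shared visit-level error. The documents do not say where in that range the analysis would fall. The main effect-size estimates are unaffected, so severity is low to moderate.

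**What to change.** 1. In the Project Description, delete the statement that mechanisms of action will be evaluated. In the Data Analysis section, delete the claim that the study can assess what drives improvement.
2. For measures taken every three weeks, report mean change visit by visit, which describes timing without imposing a straight line.
3. For all measures, including the four taken only at weeks 0 and 12, report the correlation of week 0 to 12 changes with a 95% confidence interval. The Project Description lists school absenteeism among the three-weekly assessments while section 1.2 gives it two time points; confirm which schedule applies.
4. Label these results as exploratory association that cannot be attributed to treatment, and extend the no-control-group caveat in section 1.6 to them.
5. If a mediator-outcome model is still fitted, name one pair in advance, lag the mediator by one visit, adjust for WEEK, use within-person estimation, and report it as association only. A ban on all such exploration is not needed.

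The cost is wording plus a short descriptive table, with no new data collection. The pilot gives up a preliminary statement about mechanism.

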1.1 Mixed models

We let $\mathbf{y}_i = (y_{i1}, \dots, y_{id})$ denote the response vector of d repeated measurements for individual $i=1, \dots, n$. For example, when modeling Peds-QL gastro the observed value y_{ij} in vector \mathbf{y}_i represents the observed value of Peds-QL gastro at week j for patient i . In a GLMM, the conditional expected value of y_{ij} is given by

$$g[E(y_{ij} | \mathbf{u})] = \mathbf{x}_{ij} \boldsymbol{\beta} + \mathbf{z}_{ij} \mathbf{u},$$

where g is the link function, \mathbf{x}_{ij} and \mathbf{z}_{ij} are vectors of observed values of explanatory variables, the parameters $\boldsymbol{\beta}$ are the fixed effects, and \mathbf{u}_i are the random effects. The LMM is a special case of GLMM for which g is the identity link function

$$E(y_{ij} | \mathbf{u}) = \mathbf{x}_{ij} \boldsymbol{\beta} + \mathbf{z}_{ij} \mathbf{u}.$$

1.1.1 Model specification

For each outcome variable with more than two measurements per patient (i.e., not only at week 0 and at week 12), we estimate the pre-post treatment effect using an LMM fitted by restricted maximum likelihood (REML). The model can be written as

$$y_{ij} = \beta_0 + \beta_1 \text{WEEK}_{ij} + u_i + \epsilon_{ij},$$

where y_{ij} represents the value of the outcome for patient i at week j , β_0 is the fixed intercept, β_1 is the fixed slope coefficient that captures the average change of the outcome variable given one more week of treatment, and u_i is the patient specific random intercept. By using random intercepts we allow patients to differ at baseline. For example, some patients might have much higher Peds-QL gastro than others at baseline.

Due to the small sample size the decision was made to not include quadratic effects or random slopes as it cause convergence issues. However, normally these should be included if they

improve the goodness of fit of the model (based on i.a. the distribution of residuals, likelihood ratio tests, or the Akaike information criterion). A model that includes both quadratic effects and random slopes can be written as

$$y_{ij} = \beta_0 + \beta_1 \text{WEEK}_{ij} + \beta_2 \text{WEEK}_{2ij} + u_{0i} + u_{1i} \text{WEEK}_{ij} + \epsilon_{ij} = \beta_0 + u_{0i} + (\beta_1 + u_{1i}) \text{WEEK}_{ij} + \beta_2 \text{WEEK}_{2ij} + \epsilon_{ij}.$$

By including a quadratic effect for weeks of treatment we account for nonlinear trends. For example, it might be that the effect of the treatment is decreasing over time. Furthermore, by including random slopes we allow for the weekly effect of the treatment to differ between patients.

For parent rated outcomes, we should also consider using a 3-level mixed model where we cluster the data by both parent and adolescent.

1.1.2 LMM estimate of Cohen's d

To obtain a standardized pre-post treatment effect (Cohen's d), the LMM estimate of the 12-week treatment effect is divided (standardized) by the standard deviation at baseline. That is, the LMM estimate of Cohen's d is defined as

$$d = 12 \times \beta_1 \text{SD}_{\text{week}=0}.$$

The confidence interval for Cohen's d is based on the LMM estimated standard errors (SE), that is

$$SE_d = 12 \times SE_{\beta_1} \text{SD}_{\text{week}=0}.$$

Standard errors can also be computed using bootstrap. This is particularly useful in case of a complex model for which Cohen's d is estimated using more than one parameter. For example, if the model includes a quadratic treatment effect, then Cohen's d is estimated as follows

$$d = 12 \times \beta_1 + 12 \times \beta_2 \text{SD}_{\text{week}=0}.$$

The standard error of Cohen's d with a quadratic treatment effect can also be calculated using the formula $Var(aX+bY) = a^2 Var(X) + b^2 Var(Y) + 2abCov(X,Y)$, where $X = \beta_1$ and $Y = \beta_2$. However, since multicollinearity can be a problem in polynomial regression which can lead to inflated standard errors, the variable for weeks of treatment should first be centralized.

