1.2 Cohen's d for paired data

Since the outcome variables for depression (CDI-S), anxiety (SCAS-S-C), quality of life of parents, and school absence only have two measurements per patient at week 0 and week 12, the decision was made to estimate the effect size for these variables using Cohen's adjusted d for paired data together with Hedges' small-sample bias correction, see Borenstein et al. (2009). It is important to note that as this estimator requires paired data only patients with an observed value at both week 0 and at week 12 can be included.

We let $(y_{i, \text{week}=0}, y_{i, \text{week}=12})$ denote a pair of observed values for some outcome variable Y at week 0 and 12 for patient i among n pairs with $d_i = y_{i, \text{week}=0} - y_{i, \text{week}=12}$. Then Cohen's d is defined as

$$d = \bar{Y}_{\text{diff}} \text{diff} S_{\text{within}} = \bar{Y}_{\text{diff}} \text{diff} / 2(1-r) \sqrt{}$$

where \bar{Y}_{diff} and S_{diff} is the mean and standard deviation of d_i , and r is the estimated correlation between weeks 0 and 12. The variance of Cohen's d is given by

$$V_d = (1/n + d^2/2n) 2(1-r).$$

To get the Hedges' corrected d , denoted g , we use the correction factor J as follows

$$g = J \times d V_g = J_2 \times V_d$$

where

$$J=1-34df-1$$

with the degrees of freedom $df=2n-2$.

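### The mixed-model Cohen's d carries no small-sample correction, which inflates it away from zero by about 2.5% at 32 patients; the paired effect sizes are already corrected

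*Combined protocol and SAP*

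**What the plan says.** Section 1.1.1 of the SAP sends every outcome with more than two measurements per patient to a linear mixed model with a random intercept and a linear week effect. Peds-QL gastro is the SAP's running example, and section 1.6 adds pain frequency. For these outcomes section 1.1.2 states that "the LMM estimate of the 12-week treatment effect is divided (standardized) by the standard deviation at baseline", so d = 12 × β1 / SD(week 0). The SE is scaled in the same way, SE_d = 12 × SE(β1) / SD(week 0). The division signs were lost when the PDF was read, but the prose settles the meaning. Neither expression contains a small-sample factor.

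Section 1.2 treats depression, anxiety, parental quality of life and school absence differently. It uses "Cohen's adjusted d for paired data together with Hedges' small-sample bias correction", that is g = J × d and V_g = J² × V_d. This estimate is standardised by S_within, and "only patients with an observed value at both week 0 and at week 12 can be included".

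The SAP does not say why one set is corrected and the other is not. The scientific summary gives effect-size estimates, needed to power a later trial, as a main product of the study.

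**The concern.** A sample SD in a denominator makes the expected ratio too large in absolute value, because the expectation of 1/SD exceeds 1/σ. Hedges' J exists to remove this, and the SAP accepts that reasoning in section 1.2. The outcomes left uncorrected include the gastrointestinal symptom and pain outcomes, for which an effect size is most likely to be carried into planning the next trial. The bias is in the point estimate. The bootstrap option in section 1.1.2 concerns standard errors, and the last-observation-carried-forward sensitivity analysis in section 1.5 leaves the week-0 SD unchanged, so neither removes it.

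**Working it through.** The documents give no numerical effect size, power or alpha, so there is no figure of the plan's own to reproduce.

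**Inputs from the documents**
- Patients at baseline: n0 = 32 (section 1.5).
- At week 12: "25 patients with no missing data at week 12" (section 1.5).
- Visits every three weeks over 12 weeks, taken as weeks 0, 3, 6, 9 and 12 (project description).
- Correction factor: J = 1 - 3/(4df - 1) (section 1.2, with the lost fraction bar restored).

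**Assumptions for the simulation:** normal data, a linear trend, equal variance at every visit, intraclass correlation (ICC) 0.3 to 0.7, true d of 0.5 or 0.8.

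**Step 1: form of the bias.** With complete, balanced normal data the estimated slope depends only on the visit means. These are independent of the sample SD at week 0. Hence E[12 × b1 / SD(week 0)] = δ / J, where δ is the true standardised change and J has n0 - 1 degrees of freedom.

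**Step 2: size.** J = 1 - 3/(4 × 31 - 1) = 1 - 3/123 = 0.9756, and 1/0.9756 = 1.025. The exact gamma-function factor is also 0.9756. The inflation is 2.5%:
- true 0.50 becomes 0.5125 on average;
- true 0.80 becomes 0.820 on average.

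**Step 3: simulation at n = 32.** The ratio of mean estimated d to true d was 1.023 to 1.027 across the settings. After multiplying by J, the mean was 0.499 to 0.501 for a true 0.5 and 0.799 to 0.800 for a true 0.8. One further run used an assumed missing-data pattern with 21 complete patients and 25 observed at week 12, as in section 1.5 (ICC 0.5, true d 0.8). It gave a ratio of 1.026.

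**Step 4: size against noise.** The simulated sampling SD of d was 0.144 to 0.221. At true 0.8 and ICC 0.5, the bias of 0.020 compares with an SD of 0.196, about one tenth.

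**Step 5: possible consequence.** Suppose the d were used directly to size a two-arm trial at 80% power and two-sided 5% (both assumed). The uncorrected and corrected values would give these numbers per arm:

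| Reported d | Uncorrected | After J |
|---|---|---|
| 0.3 | 175 | 184 |
| 0.5 | 63 | 66 |
| 0.8 | 25 | 26 |

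**Step 6: what J leaves alone.** SE_d treats the baseline SD as known. At ICC 0.6 and d = 0.8 it equals 12 × √0.4 / √(32 × 90) = 0.141, where 90 is the sum of squared deviations of the five visit weeks from their mean. The simulated sampling SD is 0.181. Multiplying both by 0.9756 gives about 0.138 and 0.177, so the relative shortfall is unchanged.

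**The case against.** The strongest reply is that nothing here is an error. Section 1.1.2 calls its quantity Cohen's d, which is uncorrected by definition. Section 1.2 calls the corrected quantity g. The SAP nowhere says that the two will be pooled or ranked. Squared bias is only about 0.4% to 1.5% of the mean squared error at n = 32. An uncontrolled pre-post d is in any case not a between-arm effect, so the per-arm numbers above only illustrate scale. Regression to the mean and dropout, both disclosed in the SAP, could bias the result far more. All of this stands, and it limits the point to a minor improvement. It does not remove a known bias that the SAP corrects elsewhere.

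Some stronger readings are tempting but not supported:
- **The bias is upward.** It is away from zero. A falling score such as pain days gives a negative slope, and d is then too negative.
- **The missing J is what makes the two sets of effect sizes incomparable.** They differ mainly in standardiser, analysis set and sign convention (slope over weeks versus week 0 minus week 12). If the week-12 SD is 0.8 to 1.4 times the baseline SD and the correlation is 0.3 to 0.7 (assumed), S_within is 0.91 to 1.29 times the baseline SD, a far larger gap than 2.5%.
- **The inflation is above 4%.** That needs 20 patients at baseline (J = 0.960). Twenty is the lower end of the recruitment target, but section 1.5 reports 32.
- **The paired correction is itself too weak because it uses 2n - 2 degrees of freedom.** Simulating 25 pairs with equal SDs and correlations from 0 to 0.8, the uncorrected paired d is inflated by 1.0% to 1.6%, and the SAP's J brings it to 0.994 to 1.000 of the truth.

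**Conclusion.** The point holds as a minor, cost-free improvement. The mixed-model d in section 1.1.2 is inflated away from zero by about 2.5% at 32 baseline patients, roughly a tenth of its sampling SD, and on its own this would not change a conclusion. The exact factor rests on normality and, strictly, on complete data. The one missing-data pattern tried gave nearly the same result. For pain frequency, which is discrete and bounded at 0 and 7, the factor is approximate. The finding concerns this one component of bias and says nothing about the net bias of an uncontrolled pre-post estimate.

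**What to change.** In section 1.1.2, report J × 12 × β1 / SD(week 0), with J = 1 - 3/(4(n0 - 1) - 1) and n0 the number of patients with a week-0 value for that outcome. Multiply SE_d by the same J. Use n0 - 1 degrees of freedom, because this SD comes from a single visit.

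Label the result as a bias-corrected d standardised by the baseline SD. Keep it separate from the paired g standardised by S_within, and state the sign convention for each. A shared Hedges' g label would hide the difference in standardiser.

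The cost is a sentence or two and one multiplication per outcome. The reported mixed-model d and its SE each shrink by about 2.4% (1 - 0.9756), with no new data or modelling. At a minimum, state that the mixed-model d is uncorrected and apply J before using it for power calculations. The treatment of the baseline SD as known in SE_d needs separate attention.
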